Subjects will also be instructed to avoid strenuous exercise for 24 hours before the FDG-PET to minimize uptake of the radiotracer in the muscles. A fingerstick will assess the blood glucose level before FDG administration to ensure it is below the specified limit (i.e. 200 mg/dl)

An intravenous catheter will be placed and will be flushed post-injection of FDG with 0.9% saline solution. Participants will receive an intravenous bolus of 5mCi (~185 MBq) of ^{18}F Fluorodeoxyglucose (FDG) by a trained technician (specifically [name] or [name], both study staff). Injection will occur coincidentally to the onset of rTMS. Dynamic scanning will begin approximately 30 minutes after this so that dynamic changes in rCMRglu can be modeled⁶⁷ during the anticipated peak effects of rTMS. Emission data will be acquired over a 45 minute period and stored in list-mode format. Data will first be sorted in the line-of-response (LOR) space and motion correction will be applied using MRI-derived motion estimates for each individual frame. Next, data will be rebinned in the sinogram space, generating prompt and random coincidences sinograms.

rTMS procedures: rTMS will be administered with a Magstim Rapid System, using a 70 mm figure-of-eight air-cooled coil. For all sessions, 20Hz stimulation will be delivered at 110% of resting motor threshold via 75 trains of 1.2 second 20Hz rTMS (i.e., 24 pulses per train), each of which will be followed by inter-train pauses of 16.8 seconds for a total of 1800 pulses (22.5 min), for a total of 1800 pulses (22.5 min). These parameters are within recommended safety limits for rTMS⁶⁸, and replicate parameters used in Eldaief et al.¹⁴ Similar rTMS durations have been shown in other paradigms to outlast the stimulation period by anywhere from 20 minutes^{53,54} to up to 1 hour.⁶⁹ During rTMS, accurate targeting of DLPFC, or the control site, will be achieved with a frameless stereotactic optical tracking neuronavigation system (Brainsight™), which will permit real-time monitoring of coil placement and head position.⁷⁰

B. Eligibility screening and baseline questionnaires:

[figure not shown]

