Specifically, subjects will undergo simultaneous resting-state (fcMRI)/FDG-PET imaging *without* rTMS at this first visit. The baseline PET session will serve as a comparison for changes in rCMRglu following rTMS. Critically, strong evidence supports the test re-test reliability across FDG-PET scanning sessions separated in time, provided that scanning parameters remain identical.⁷¹⁻⁷⁴ Therefore, observed metabolic changes after rTMS will be attributable to the stimulation, and will be deemed unlikely to occur as a result of inherent variability across scanning sessions. Baseline fcMRI data will serve the purpose of creating functional connectivity maps from a sgACC seed. Similar to how lpIPL was designated in Eldaief et al.¹⁴, these maps will be used to establish two cortical targets for rTMS in DLPFC: one which is positively correlated to sgACC, and another which is anticorrelated to sgACC^{21,22} (**Fig 1**). After their baseline visit, subjects will return for the first of two rTMS sessions in which they will receive 20Hz stimulation to either the positively or negatively correlated left DLPFC region. They will then return for a third session in which the alternate region is stimulated (thus enabling a within-subject design). Subjects will be randomized to a given session order, and this order will be counterbalanced across subjects. It is expected that all three visits will be completed within two months from the time of enrollment. The experimental timeline for the rTMS sessions is depicted in **Fig 5**. Immediately before stimulation subjects will be rapidly scanned with resting-state fMRI *without* PET (for approx. 25 minutes). After this, they will fill out a brief (1 min) visual analog scale in which they rate sadness, anxiety, energy, concentration, happiness, anger and disgust on a scale of 0-10. They will then be taken into a room immediately adjacent to the scanner for rTMS (i.e. constituting “off-line” stimulation⁷⁵). Subjects will be injected with FDG concurrent to the onset of rTMS. After rTMS they will again complete the mood analog scale. They will then be promptly returned to the scanner room for PET/fcMRI (within ~5 min) so as to acquire BOLD data as soon as possible after rTMS.¹⁴ Dynamic PET acquisitions will correspondingly begin at this time (e.g. at approx. 30-35 min post FDG injection), and emission data will be collected for the next 45 min.

	Visit 1	Visit 2	Visit 3	Visit 4
Obtainment of Consent	X			

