Experimental Controls: To ensure that the effects of rTMS are specific to the cortico-limbic systems investigated, we will construct three extra-network seed regions: primary motor cortex (M1), primary auditory cortex (A1) and primary visual cortex (V1). A lack of rTMS induced changes in rCMRglu in these regions; and a lack of rTMS induced changes in inter-hemispheric functional connectivity between these regions, will corroborate network specific effects. To ensure that the effects of rTMS are not the result of inherent variability of connectivity between two fMRI acquisitions separated in time, we will compare *pre*-rTMS fMRI scans between the two stimulation sessions (correlated and anticorrelated). A lack of significant variability between these will argue that changes were caused by rTMS (identical controls were used in Eldaief et al.¹⁴)

Rating scales: Paired t-tests will compare mood analog scale ratings before and after rTMS to assess the possibility that stimulation of cortico-limbic networks confers transient mood altering effects.

VII. RISKS AND DISCOMFORTS

Risks attributable to MRI: There are no known or foreseeable risks associated with conventional MRI procedures except to those people who have electrically, magnetically or mechanically activated implants (such as cardiac pacemakers), or those who have cerebrovascular clips. Participants will therefore be screened very carefully (with a standardized MRI screening form-see attachment) to exclude the possibility that they have any such devices and/or implants, and will be excluded from participation in the event that they do. There are no known additional risks associated with functional MRI, and the functional MRI systems to be employed have been approved by the FDA and will be operated within the standards reviewed and accepted by the FDA. All studies will specifically adhere to these FDA approved safety levels for the Siemens system. These safety parameters include static magnetic field, time varying magnetic fields (dB/dt), specific absorption rate (SAR), and acoustic noise levels. Subjects will be informed about minimal risks of routine high magnetic field and non-ionizing RF radiation involved in MR imaging. Still, an MRI might be uncomfortable to a subject due to the risk of a) claustrophobia; b) boredom from lying still for an extended time or c) being perturbed by scanner noise.

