In terms of seizures, all rTMS sessions will be conducted by the PI ([name]) who is (1) a board certified neurologist, (2) has been trained in the safe and efficient administration of TMS (through a course offered at the Berenson-Allen Center for Non-Invasive Brain Stimulation at the Beth Israel Deaconess Medical Center) and (3) is trained in basic life support and in the recognition and treatment of convulsions, syncope and other medical/neurological emergencies. In addition, a fully equipped and regularly checked crash cart will be available at all sites where TMS stimulation will occur. This emergency equipment includes oxygen supply, IV line supplies, and emergency medications (e.g. benzodiazepines) in the event of a convulsion. Therefore, should any complication occur, rapid medical coverage for the subject will be provided, followed by Emergency Room care if appropriate. We will also monitor patients in detail during and after delivery of rTMS, using an approach drawn directly from suggested guidelines.⁶⁸ Notably, there is not expected to be an increase in the risk of seizures with stimulation of the control site. In fact, stimulation of the cerebellum is much less likely to result in seizure induction. Other measures to minimize risks from TMS are listed in **Table 2**.

Risk Associated with TMS	Measures taken to prevent/minimize this risk
20-40% of subjects experience MILD headaches or neck pain	Care will be taken to administer stimulation in a comfortable neck position and to avoid unnecessary stimulation of neck/scalp muscles.
TMS produces a loud clicking sound which may cause tinnitus or rarely short-term hearing loss	Subjects will be given earplugs, which, in animal and human studies, proven effective in preventing the risk of hearing disturbance due to TMS.
TMS could induce short-term changes in memory, attention and other cognitive functions	This is a theoretical risk, as none of the safety studies conducted has found such side effects.
Acute psychiatric effects such as mania and delusions have been described in patients with medically refractory depression or bipolar disorder who received rTMS. This seems to be a rare complication of rTMS (incidence <0.15% of patients).	Mania and delusions arising from TMS have not been described in purely schizophrenic cohorts, e.g. those without a comorbid affective disorder. Subjects will undergo a brief rTMS side effects questionnaire after rTMS to assess for these rare effects.

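### The PET specificity check counts primary auditory cortex as a no-change region, although FDG is taken up during loud rTMS clicks that the baseline scan lacks

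*Protocol*

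**What the plan says.** Protocol Section VI (Experimental Controls) sets up three seeds outside the cortico-limbic system: "primary motor cortex (M1), primary auditory cortex (A1) and primary visual cortex (V1". Two findings there are to corroborate network specificity. One is metabolic, "A lack of rTMS induced changes in rCMRglu in these regions". The other is an absence of change in inter-hemispheric connectivity.

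Section VI (FDG-PET data) defines the metabolic change within a person as post-rTMS PET against baseline PET. Section V.C and Table 1 place that baseline at visit 1, without rTMS.

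On timing, Section V.A (PET procedures) states "Injection will occur coincidentally to the onset of rTMS", and Section V.C repeats it: "Subjects will be injected with FDG concurrent to the onset of rTMS". Section V.C puts the start of PET acquisition at about 30 to 35 minutes after injection. Section V.A (rTMS procedures) gives the stimulation as "75 trains of 1.2 second 20Hz rTMS (i.e., 24 pulses per train", with "inter-train pauses of 16.8 seconds".

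On sound, Table 2 in Section VII states "TMS produces a loud clicking sound which may cause tinnitus or rarely short-term hearing loss" and lists earplugs as the protective measure.

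**The concern.** A negative-control region should be one that the intervention can reach only by the route being ruled out, here a spread of stimulation beyond the targeted network. A1 does not meet that condition in the baseline-referenced PET contrast. It is the primary cortex for the one sensory input that the protocol describes as loud. That input is present during tracer uptake in the rTMS sessions and absent at baseline. The protocol describes no sham coil, recorded click or masking noise for the baseline uptake.

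If A1 metabolism rises because the participant hears the coil, the plan has no way to recognise this. Section V.C states that metabolic changes after rTMS will be put down to the stimulation. The support that the check is meant to give to a DLPFC or sgACC effect would then be withheld for a reason unrelated to network spread.

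**Working it through.** **1. The protocol's session figures reproduce** (inputs from Section V.A, rTMS procedures).
- Pulses: 75 × 24 = 1800.
- Duration: 75 × (1.2 + 16.8) s = 1350 s = 22.5 min.

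Both agree with the stated totals.

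**2. Share of the pre-scan uptake period covered by the session** (scan start at 30 to 35 min, Section V.C).
- At 30 min: 22.5 / 30 = 75%.
- At 35 min: 22.5 / 35 = 64%.
- At baseline: 0%, since there is no rTMS.

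**3. Time in which pulses actually sound.**
- 75 × 1.2 s = 90 s.
- Share of the session: 90 / 1350 = 6.7%.
- Share of the pre-scan period: 90 / 1800 = 5.0% at 30 min, and 90 / 2100 = 4.3% at 35 min.

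The clicks are therefore intermittent, one train every 18 s, but they recur through most of the uptake period.

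**4. Which parts of the check are exposed.**

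| Check | Comparison | Clicks during the measurement? |
|---|---|---|
| A1 rCMRglu | baseline PET vs post-rTMS PET | during uptake in the second scan only |
| M1 and V1 rCMRglu | same | same clicks, but not auditory cortex |
| Inter-hemispheric connectivity | BOLD before vs after rTMS | no, BOLD is not acquired during rTMS |
| A1 rCMRglu between the two DLPFC sessions | post-rTMS vs post-rTMS | yes in both, with the same number and rate |

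Only the first row has the problem.

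**5. How small a sound effect could register (illustration only).** The documents give no size for an auditory response in A1. As an assumption, take the SD of 2.77% that Section III.D quotes for rCMRglu change after high-frequency rTMS, and apply it to A1 change scores. For a two-sided paired t-test at 5% with n = 25 (24 df), the noncentrality is Δ × √25 / 2.77.

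| A1 change Δ | Noncentrality | Power |
|---|---|---|
| 1% | 1.81 | 41% |
| 1.5% | 2.71 | 74% |
| 2% | 3.61 | 93% |
| 3% | 5.42 | over 99% |

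The change detectable with 90% power is about 1.9%. This range shows what the check could pick up. It does not predict what sound will do.

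**The case against.** The strongest reply is that this is a supporting check that works in one direction. Section VI says that no change in three regions, together with no connectivity change, corroborates specificity. It sets no pass/fail rule, and it does not say that a change in A1 makes a DLPFC or sgACC effect non-specific. This stands. A reader might infer that any A1 response would be counted in full against specificity, but no sentence in the protocol says so.

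A second reply is that the likely error is conservative. A sound-driven rise in A1 leads to withheld support, and would not readily produce a false claim of specificity. This also stands. It answers a further tempting reading, that A1 is uninformative whichever way it turns out. If earplugs dampen the sound and A1 does not change, that result still carries some of the meaning the protocol intends.

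Third, earplugs are planned and pulses sound for only 90 s. Both points lower the expected effect. However, Table 2 offers earplugs to protect hearing. It does not say that they make the clicks inaudible or match the sound at baseline. The sound conditions during baseline uptake are not stated, so some other auditory difference, of unknown direction, is also possible.

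Fourth, the main PET questions are largely protected. Contrasts between stimulation sites and between patients and controls (Section VI; Hypotheses 2.2 and 2.4) compare sessions with the same pulse count and timing, so sound largely cancels. This stands. Control-site stimulation under Hypothesis 2.5 would also produce clicks. However, the fourth visit is optional and limited to five participants (Section V.C), and Section VI does not make it the reference for the A1 check.

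**Conclusion.** The point holds in a limited form. As written, the plan uses A1 as a no-change region in a PET contrast where one scan's uptake period contains 1800 loud clicks and the other's contains none. The session fills 64% to 75% of the time from injection to scan, with 90 s of pulse trains. An A1 increase could arise from sound alone and would then wrongly withhold support for network specificity.

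The conclusion rests on the protocol's own statements about injection timing, click loudness and the baseline scan. It also assumes that earplugs leave the clicks at least partly audible. The size of any A1 response is unknown.

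The scope is one of three regions in one supporting PET check. The argument does not reach M1, V1 or the connectivity checks, and it alters no primary outcome, sample size or main contrast. The documents do not support reading it as a threat to the DLPFC or sgACC findings themselves.

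**What to change.** In Section VI (Experimental Controls):

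- Base the baseline-referenced PET specificity check on M1 and V1.
- Report the baseline-to-post-rTMS change in A1 rCMRglu separately, labelled as possibly auditory, and not as evidence for or against network specificity.
- Keep A1 inter-hemispheric connectivity as planned.

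A comparison of A1 rCMRglu between the two DLPFC sessions may be added as a supporting analysis, since click number and rate are matched there. It should not replace the baseline-referenced check, because it cancels any non-specific spread common to both sites along with the sound. The match may also be imperfect: Section I notes that the anticorrelated site tends to be more lateral, so the distance from coil to ear may differ.

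The cost is a few sentences, with no new data or procedures, and one region fewer in a supporting PET check.

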7. Any subject who has known metallic or ferromagnetic bioimplants, or who has a history of seizures or a first degree relative with seizures, or who has a history of significant claustrophobia.
- D. *Sample Size Determination:* Sample size calculations for the rTMS/fMRI studies are based on Eldaief et al, as we are unaware of other studies that provide empirical estimates of effect size. The main outcome measure for the TMS/fMRI experiments will be a change (pre vs. post-rTMS) in correlation values (z) between sgACC and DLPFC. Our study of 17 subjects yielded an effect size of 0.15 for 20Hz rTMS induced changes between lplPL and mPFC (SD=0.11). Based on this, sample sizes of 8 and 12 would have enough power (90%) to detect changes similar to those observed in our prior study at a significance level of 5% using an unpaired t-test or a paired t-test, respectively. With respect to PET, a comparable FDG-PET study⁶⁶ found an average change in rCMRglu of 5.3% (SD=2.77%) following high frequency rTMS. Based on this, sample sizes of 5 and 7 would be required (power, 90%; α , 0.05; unpaired and paired t-tests, respectively). However, because these effect sizes were all calculated from healthy controls, they might represent underestimates of the effect sizes needed for MDD patients. Therefore, we will conservatively recruit 25 subjects for each subject group.

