interest will be DLPFC-sgACC. Based on prior studies,^{1-9,30} secondary correlation pairs of interest will be sgACC-dmPFC, sgACC-NA and sgACC-amygdala. fMRI data will be analyzed using a combination of software packages (e.g., FMRIB Software Library, FSL, Freesurfer, SPM) and custom software developed in the [name] (mentor) lab. These methods have been described in several other paradigms^{27-29,76,77} and were employed in Eldaief et al.¹⁴ We will apply a stringent in-house data quality control program to each dataset, described Yeo et al.,⁷⁸ to evaluate fMRI runs for low signal-to-noise and/or excessive head movement. Preprocessing will include global mean regression and temporal band-passing of data for signals >0.08 Hz. After preprocessing, region-to-region correlation strengths will be calculated with volumetric seed-based functional connectivity analyses: correlation maps will be produced by extracting the BOLD time course from a “seed” ROI in the brain, and then computing the Pearson's correlation coefficient (r) between that time course and the time course from all other brain voxels. Functional connectivity between two ROIs will be measured by r values, which will be transformed to the z distribution. Paired t-tests will directly compare changes in z scores before and after rTMS in a given individual, and two-sample paired t-tests will compare changes across conditions and across subjects.

FDG-PET data: MR-based motion estimates and a dual-echo ultrashort echo time MRI sequence (DUTE)⁷⁹ will be used for motion- and attenuation-correction of PET data, respectively. Other preprocessing steps will include image realignment, normalization to MNI space and smoothing. Weighted linear contrasts will then be used to identify changes in rCMRglu in the cortico-limbic regions of interest described above. Relative differences in normalized rCMRglu in these ROIs between the baseline PET scan and the post-rTMS PET scan within a given individual will be calculated on a voxel-by-voxel basis using a paired t-test. Two sample paired t-tests will compare rCMRglu changes across rTMS conditions, and across MDD patients and normals. The experimental PET and fMRI data revealing local and distributed impacts of TMS will also allow for computational analyses which will be developed with the supervision and guidance of [name] (advisor).

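### The connectivity check for network specificity uses only region pairs that contain neither the stimulated DLPFC nor sgACC, so it cannot detect a change in their coupling with regions outside the network

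*Protocol*

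**What the plan says.** Section III.D of the protocol (Sample Size Determination) names the effect of interest: "The main outcome measure for the TMS/fMRI experiments will be a change (pre vs. post-rTMS) in correlation values (z) between sgACC and DLPFC". Section VI, fcMRI data, repeats DLPFC-sgACC as the primary pair and adds that "secondary correlation pairs of interest will be sgACC-dmPFC, sgACC-NA and sgACC-amygdala". Every pair in the outcome analysis lies within the cortico-limbic set.

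Specificity is handled in Section VI under Experimental Controls: "To ensure that the effects of rTMS are specific to the cortico-limbic systems investigated, we will construct three extra-network seed regions". The regions are primary motor (M1), auditory (A1) and visual (V1) cortex. Two findings are to count as support. One is metabolic: "A lack of rTMS induced changes in rCMRglu in these regions". The other is the only connectivity criterion: "a lack of rTMS induced changes in inter-hemispheric functional connectivity between these regions, will corroborate network specific effects".

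The fcMRI paragraph also plans correlation maps from each seed to all other voxels, after preprocessing that includes global mean regression. No specificity criterion is attached to those maps.

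**The concern.** The claim to be supported is selectivity: that stimulation changed DLPFC-sgACC coupling and did not simply change how DLPFC, or sgACC, couples with other regions in general. To test it, one of those two nodes must be paired with something outside the network. The planned control pairs share no node with the outcome.

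The rival explanation is the protocol's own. The Preliminary data part of Section I allows that the connectivity changes in the earlier study may have been driven mainly by altered excitability at the stimulated node, and Hypothesis 2.1 predicts a local metabolic rise at both DLPFC sites. An effect centred on the stimulated node is thus plausible, and this check does not look for it. At stake is the wording of the specificity conclusion, not the primary result.

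**Working it through.** **1. Which nodes appear where.** No figure in the protocol bears on this point, so the first step is to set the pairs side by side.

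- Primary outcome: DLPFC-sgACC.
- Secondary outcomes: sgACC-dmPFC, sgACC-NA, sgACC-amygdala.
- Connectivity control: inter-hemispheric pairs among M1, A1 and V1.

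Whether the control wording means left-right pairs of the same region or also cross-hemisphere pairs of different regions, DLPFC and sgACC are absent.

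**2. Whether another planned control fills the gap.**

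| Control | Where | What it addresses |
|---|---|---|
| rCMRglu in M1, A1, V1 | VI, Experimental Controls | Local metabolism; DLPFC coupling with these regions can change without it |
| Pre-rTMS scans compared between sessions | VI, Experimental Controls | Variability over time |
| Correlated vs anticorrelated site | VI, fcMRI data | Difference between two sites; each effect could be non-selective, with different size |
| Parietal or cerebellar control site | II, Hypothesis 2.5 | Coil location; the optional fourth visit, apparently this session, has at most five subjects (V.C) |
| Seed-to-voxel maps | VI, fcMRI data | Could show the change, but no specificity criterion uses them |

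None tests DLPFC or sgACC coupling with an extra-network region.

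**3. Why the control pairs cannot respond.** Suppose stimulation weakens the DLPFC signal D: D' = aD + sqrt(1 - a²)·SD(D)·e, with e independent noise. Then corr(D', X) = a·corr(D, X) for every region X, while the correlation of left with right M1 contains no D and does not move. Global mean regression modifies this only indirectly, through DLPFC's share of the global mean.

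**4. Simulation.** All values except the group size are assumptions: a = 0.6, 60 regions, 360 time points, 200 replicates, and a DLPFC that shares some signal with M1, A1 and V1 before stimulation. There are 25 subjects, as in one group of Section III.D. Tests are paired t-tests on Fisher z, two-sided 0.05.

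| Pair | Mean change in z, with global mean regression | Significant | Mean change, without | Significant |
|---|---|---|---|---|
| DLPFC-sgACC | -0.205 | 100% | -0.282 | 100% |
| DLPFC-M1 | -0.088 | 100% | -0.156 | 100% |
| DLPFC-A1 | -0.091 | 100% | -0.155 | 100% |
| DLPFC-V1 | -0.091 | 100% | -0.155 | 100% |
| M1 left-right | 0.002 | 5% | 0.001 | 4% |
| A1 left-right | 0.001 | 7% | 0.000 | 5% |
| V1 left-right | 0.002 | 4.5% | 0.000 | 7.5% |

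The planned pairs reject at about the nominal level; the omitted pairs show the change.

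**5. What a contrast can and cannot do.** With global mean regression, the mean DLPFC-control change is (-0.088 - 0.091 - 0.091)/3 = -0.090. The contrast is -0.205 - (-0.090) = -0.115, not zero, although the effect was built to be non-selective. Scaling by a common factor shrinks larger correlations more. The control-pair changes must therefore be read alongside any contrast.

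**The case against.** The left-right pairs are a legitimate control. They detect diffuse change in the control regions from arousal, motion or the scanner, and should stay. The seed-to-voxel maps are also relevant: the earlier study, whose methods are reused, displayed voxelwise maps of connectivity change (Section I, Fig 2), and in such maps a change in DLPFC coupling with M1, A1 or V1 could be seen. That stands as a reason to expect that an attentive analyst might notice the problem. It does not repair the stated rule, which draws its conclusion from the inter-hemispheric pairs and rCMRglu alone.

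It can also be said that supplementary control pairs belong in a statistical analysis plan, which is not shown. That would answer a complaint about missing detail. Here the protocol itself states both the check and the conclusion it supports, and the second does not follow from the first.

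Finally, a contrast against control pairs is not a clean test of selectivity either, as step 5 of the working shows. This is correct, and it shapes the fix: the contrast cannot carry the claim alone.

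**Conclusion.** The point holds in a limited form. The connectivity check can exclude a diffuse change in M1, A1 and V1. It cannot exclude a change in DLPFC or sgACC coupling with regions outside the network, so a non-selective effect could be taken as network-specific. The primary outcome, its test and the sample size are not affected.

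A reader might infer more: that an equal shift in DLPFC coupling with the whole brain would pass and would be reported as network-specific. The documents do not support this. Global mean regression makes an equal whole-brain shift an unrealistic result after preprocessing, and the protocol says only that the findings will corroborate specificity; it sets no pass/fail rule. For the same reasons, no probability of a false specificity claim can be derived from the protocol.

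That the control pairs omit both nodes rests on the text alone. The sizes rest on the assumed simulation, in particular on DLPFC having some coupling with M1, A1 and V1 to lose. Where that coupling is near zero, weakening of the DLPFC signal would show little in the added pairs.

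**What to change.** In Section VI, Experimental Controls:

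- Add the pairs stimulated DLPFC-M1, -A1, -V1 and sgACC-M1, -A1, -V1 from the seeds already built, and report their pre-to-post changes in z with confidence intervals.
- Base the specificity statement on these changes together with two within-session contrasts, both required: DLPFC-sgACC change minus mean DLPFC-control change, and DLPFC-sgACC change minus mean sgACC-control change.
- Do not pool the two comparators. For illustration, take the 0.15 of Section III.D as the change in DLPFC-sgACC and in all three DLPFC-control pairs, with the sgACC-control pairs unchanged. The pooled comparator is (3 × 0.15 + 3 × 0)/6 = 0.075 and the pooled contrast 0.15 - 0.075 = 0.075, which would wrongly suggest selectivity. The separate DLPFC contrast is 0.15 - 0.15 = 0.
- State that a non-zero contrast is not to be read as specificity when the control pairs have also clearly changed.
- Keep the inter-hemispheric pairs and rCMRglu in M1, A1 and V1 as a check for diffuse change only.

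The cost is a few extra correlations from data already planned, with no new scans. The specificity claim may become harder to make.

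### Before/after t-tests on the mood scale cannot tie a change to cortico-limbic stimulation; the between-target contrast already planned for imaging should be added

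*Protocol*

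**What the plan says.** Section V.C of the protocol (Aim 1 and 2 Experimental Procedures) has subjects complete a one-minute visual analog scale at each rTMS visit, straight after the pre-stimulation scan. They are to "rate sadness, anxiety, energy, concentration, happiness, anger and disgust on a scale of 0-10". They then move to an adjacent room, receive FDG as rTMS starts, and have the stimulation. The second rating follows: "After rTMS they will again complete the mood analog scale".

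Section VI, Rating scales, gives the whole mood analysis in one sentence: "Paired t-tests will compare mood analog scale ratings before and after rTMS to assess the possibility that stimulation of cortico-limbic networks confers" transient effects on mood. It names no comparison between targets, between groups or with a control site.

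The design does provide two sessions per subject. Of the visit after the first rTMS session, Section V.C says: "They will then return for a third session in which the alternate region is stimulated (thus enabling a within-subject design"). It adds: "Subjects will be randomized to a given session order, and this order will be counterbalanced across subjects". For fcMRI and for PET, Section VI compares the changes across the two stimulation conditions and across patients and controls.

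**The concern.** The stated purpose is attribution: whether stimulating these networks alters mood. A before/after test supports that only if mood would otherwise have stayed still between the two ratings, and the protocol gives several reasons to doubt this.

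- The first rating comes after about 25 minutes in the scanner. Section VII lists claustrophobia, boredom and noise as possible discomforts of MRI.
- The second rating follows an FDG injection and 22.5 minutes of rTMS. Table 2 in Section VII says that "20-40% of subjects experience MILD headaches or neck pain" and describes a loud clicking noise.
- Section V.A applies the same active 20 Hz regimen in all sessions, and no sham session is described.

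Relief, fatigue, discomfort or expectancy could move items such as anxiety, energy, concentration or anger with no network effect at all. A significant before/after difference could then be read as a mood effect of network stimulation. A difference between the two targets, for which the ratings are collected, has no test in the plan.

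**Working it through.** **No figure to reproduce.** The protocol states no effect size, SD or power for the mood scale. Sample Size Determination (Section III.D) covers imaging only. What follows is an illustration with assumed shifts, shown over a range.

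**Inputs from the protocol**
- 25 subjects per group, 50 in total (Section V.C).
- A 5% two-sided level. Section III.D states 5% for the imaging outcomes; using it for mood, and two-sided, is an assumption.
- Time from start to end of rTMS: 75 trains × (1.2 + 16.8) s = 1,350 s = 22.5 min (Section V.A).

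**Assumed inputs**
- A non-specific shift δ of 0.2, 0.3, 0.5 or 0.8, in units of the SD of the before-to-after change.
- A correlation ρ between a subject's changes in the two sessions, from 0 to 0.7.

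**Step 1: the planned test.** Suppose stimulation has no effect on mood but ratings shift by δ for other reasons. The paired t statistic then follows a noncentral t distribution with n − 1 degrees of freedom and noncentrality λ = δ√n. The chance that one item at one session is significant is:

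| δ | λ, n = 25 | Rejects, n = 25 | λ, n = 50 (groups pooled) | Rejects, n = 50 |
|---|---|---|---|---|
| 0.2 | 1.0 | 16% | 1.41 | 28% |
| 0.3 | 1.5 | 30% | 2.12 | 55% |
| 0.5 | 2.5 | 67% | 3.54 | 93% |
| 0.8 | 4.0 | 97% | 5.66 | about 100% |

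**Step 2: the between-target contrast.** Let D be the change at the correlated target minus the change at the anticorrelated target, in the same subject. If the shift is δ at both, the mean of D is δ − δ = 0, and the test rejects at its nominal 5% whatever δ is. A simulation with δ = 0.5, ρ = 0.5, n = 25 and 20,000 runs gave 67.2% rejection for the before/after test and 5.0% for the contrast.

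**Step 3: what the contrast can detect.** The SD of D is √(2(1 − ρ)) times the SD of change. At 80% power a paired test detects 0.584 SD of the tested difference at n = 25, and 0.404 SD at n = 50. In units of the SD of change:

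| ρ | √(2(1 − ρ)) | n = 25 | n = 50 |
|---|---|---|---|
| 0 | 1.414 | 0.83 | 0.57 |
| 0.3 | 1.183 | 0.69 | 0.48 |
| 0.5 | 1.000 | 0.58 | 0.40 |
| 0.7 | 0.775 | 0.45 | 0.31 |

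**Step 4: if the shift is not equal at both targets.** With ρ = 0.5 the SD of D equals the SD of change, so the rows of Step 1 apply to the difference in shifts. A difference of 0.2 SD would make the contrast reject 16% of the time at n = 25, instead of 5%.

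**Step 5: the off-network control site.** Hypothesis 2.5 names a parietal or cerebellar site. It appears to belong to the optional fourth visit, offered to at most five subjects (Section V.C). At n = 5, 80% power needs a difference of about 1.7 SD.

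**The case against.** The strongest reply is that the contrast answers another question. Section VI asks whether cortico-limbic stimulation alters mood. Both targets are DLPFC sites chosen for their connectivity with sgACC, and both get active 20 Hz stimulation, so any mood effect they share cancels in the contrast. Nor need the non-specific shift be equal: Section I says anticorrelated sites tend to lie more laterally, so scalp discomfort might differ. Mood is not among the outcomes listed in Section I, no hypothesis in Section II concerns it, and Section VI speaks only of a possibility. Discomfort is recorded separately by a side-effects questionnaire after each rTMS session.

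All of this stands. It limits what the contrast can show and how much the point matters. It does not rescue the before/after test: the protocol itself chose that test and attached an attribution that the test cannot carry, so this is not a detail left to an SAP.

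A reader might infer three stronger points that the protocol does not support.

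- **That the two-target design already supplies a control.** Each target is only an active comparator for the other.
- **That 28 tests will be run.** 7 items × 2 targets × 2 groups = 28 gives 28 × 0.05 = 1.4 expected false positives, and 1 − 0.95^28 = 76% for at least one. The protocol does not state that split. Pooled over targets and groups, 7 tests give 1 − 0.95^7 = 30%. Both percentages assume independent items, and mood items are probably correlated. Multiplicity may also be handled in an SAP that is not at hand.
- **That subjects are unblinded to target.** The protocol is silent on this.

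**Conclusion.** The point holds in a limited form. The planned before/after tests cannot separate an effect of stimulation on mood from a non-specific change between the two ratings. Under assumed shifts of 0.2 to 0.8 SD of change, one test at n = 25 rejects between about 16% and 97% of the time with no stimulation effect. The between-target contrast stays at 5%, provided that the shift is the same at both targets. The protocol gives no mood data from which to choose a value within that range.

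The contrast isolates only a difference between targets. A mood effect common to both cannot be attributed without sham or off-network data, and at most five control-site subjects cannot fill that gap. No listed primary or secondary outcome is affected, so this is a cheap improvement and not a threat to the trial's main conclusions.

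**What to change.** Amend the Rating scales paragraph of Section VI, or settle it in the SAP:

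- Alongside the before/after comparisons, add for each item the within-subject contrast of before-to-after change at the correlated versus the anticorrelated target, allowing for session order.
- Compare the changes between patients and controls, as Section VI does for fcMRI and PET. A group difference could still reflect a different non-specific response, so it should be read with that reservation.
- Present the before/after changes as descriptive and do not attribute them to network stimulation.
- State that the two targets are active comparators, and that an effect shared by both cannot be attributed from these data.

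The cost is one paragraph of text, with no new visits, subjects or measurements. The downside is that a mood effect shared by both targets would be described but not attributed.
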